7.0 STATISTICAL ANALYSIS PLAN

7.1 Statistical Analysis Plan Summary

Power Calculation

This is a phase II trial investigating adjuvant pembrolizumab after completion of radiation +/- concomitant cytotoxic chemotherapy in the treatment of stage IVB ATC. The primary endpoint is the progression-free survival (PFS), which is from the start of the adjuvant pembrolizumab till the disease progression or completion of follow-up. We will estimate the median PFS and focus on unresected patients from cohort 1 and 2 for our primary analysis and futility monitoring. Resected patients from cohort 3 will serve as patients for exploratory analysis. Based on historical data, the median PFS for unresected patients is 6.8 months. We anticipate unresected patients under adjuvant pembrolizumab will improve their median PFS to be 10.5 months. Assuming an accrual rate is one patient per month and 12 months additional follow-up after the last patient being enrolled, with 30 evaluable patients we would have 80.0% power using 1-sided 10% alpha for a one-sample log rank test (calculated using trialdesign.org). The required number of events is 24 and exponential survival time is assumed.

Futility Monitoring

We will enroll at least 10 subjects and at most 30 (cohorts 1 and 2 will enroll 15 subjects each) subjects at a rate of one patient per month and we will follow all patients for at least 12 months for the purposes of the futility monitoring rule. We will use the methods described by Thall et al. [14] to monitor progression-free survival from the date of start of adjuvant pembrolizumab and will stop enrolling subjects early if, based on the available data, we have reason to believe that the median PFS is less than that observed by historical therapy (i.e, 6.8 months). Formally, we will stop enrolling patients early if:

$$\Pr(\text{median PFS}_{\text{experimental}} > \text{median PFS}_{\text{historical}} \mid \text{data from the trial}) < 0.05.$$

That is, if there is less than 5% chance that the median PFS is more than that observed with historical therapy (6.8 months), then we will stop enrolling subjects. Details of how this monitoring rule was constructed are explained in the “*Technical Details*” section below. The operating characteristics of this monitoring rule are shown in the table below and are based on 1,000 simulations of the monitoring rule using the One-Arm Time-to-Event Simulator (PID-359): Version 3.0.9. developed in the Department of

Biostatistics at MD Anderson and available at the following website (<https://biostatistics.mdanderson.org/SoftwareDownload/>).

Table 6. Operating characteristics of the futility monitoring rule

Scenario	True Median PFS (Months)	Pr(Stop Early)	Mean # Patients	Trial Duration (Months)
1	1	>0.99	10.00	22.20
2	3	0.99	12.49	25.23
3	6	0.23	26.46	38.92
4	7	0.11	28.19	40.55
5	10	0.01	29.75	42.06
6	11	0.01	29.84	42.04
7	12	<0.01	29.92	42.11

We will use the Clinical Trial Conduct (CTC) website, which is housed on a secure server at MD Anderson and maintained by the Department of Biostatistics, to implement the futility monitoring rule. The CTC website is found at <https://biostatistics.mdanderson.org/ClinicalTrialConduct/>. Access to the CTC website will be gained through usernames and passwords provided by the MD Anderson Department of Biostatistics to study personnel responsible for enrolling patients and updating, reviewing, and analyzing patient data. Training on the use of the CTC website will be provided by the study statisticians, with

Pembrolizumab MISP Protocol Template

47

Version 11.0: 12-October-2020

Protocol Version Date: December 6, 2023

particular attention to the importance of timely updating of follow-up dates and recording events. Monitoring will occur at each patient accrual so all previous patient's data will be updated at each patient accrual.

Technical details

At any point in the trial the PFS can be calculate for each patient, with the time interval regarded as censored at the date of last clinic-visit assessed for progression if the patient is still alive without progressive disease. At each interim analysis, we will apply a Bayesian method for updating prior information with PFS observed at that time. We assume that the PFS for each patient is exponentially distributed with a median of λ_H months for the historical treatment and a median of λ_E for the experimental treatment. We assume λ_H follows an inverse gamma distribution with mean 6.8 months and standard deviation of 1 month. The middle 95% of this distribution is between 5.12 and 9.02 months. We assume λ_E follows an inverse gamma distribution with mean 6.8 months and standard deviation of 10 months. The middle 95% of this distribution is between 1.57 and 24.77months.

The goal of the futility monitoring rule is to guard against a median PFS rate less than that observed by historical therapy. Patients enrolled will be stopped early if based on the available data, $\Pr(\lambda_E > \lambda_H \mid \text{data from the trial}) < 0.05$. This rule was chosen to achieve a high early-stopping probability if the true median PFS is less than 6.8 months for the experimental treatment, while maintaining a relatively low early-stopping probability if the median PFS is greater than 6.8 months for the experimental treatment.

Analysis

We will use descriptive statistics to summarize the demographic and clinical characteristics of the subjects. Cohorts 1 and 2 will consist of our primary analysis set. We will estimate the median PFS with a 95% confidence interval and report the posterior probability that the median PFS is > 6.8 months. We will also estimate PFS with the methods of Kaplan and Meier and model PFS as a function of potential prognostic factors using Cox proportional hazards regression. PFS will be calculated as the time from date of start of pembrolizumab to the earliest date of last clinic visit assessed for progression, date of progression, or date of death. Secondary objectives consist of overall survival and disease-free survival. OS will be calculated as the time from date of start of pembrolizumab to the earliest date of death or last conduct. DFS will be calculated as time from disease-free status to earliest date of last clinic visit assessed for disease, date of recurrence, date of metastasis, or date of death. OS and DFS will analyzed similarly as PFS. Cohort 3 will include 5 subjects and will be analyzed descriptively.

Evaluable Analysis Set: Our evaluable patient population will be subjects who start pembrolizumab and have one follow up imaging visit to assess for disease progression. Subjects who do not start pembrolizumab will be replaced.

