6.1.4.2 Tumor Imaging During the Study

The first on-study imaging assessment should be performed at 6 weeks ([42] days \pm 7 days) from the date of first dose of pembrolizumab. Subsequent tumor imaging should be performed every 12 weeks ([84] days \pm 7 days) or more frequently if clinically indicated. Imaging timing should follow calendar days and should not be adjusted for delays in cycle starts. Imaging should continue to be performed until disease progression is identified by the Investigator.

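### The SAP says the futility rule is likely to stop whenever the true median PFS is below 6.8 months, but stopping is likely only at about 4 months or less, and Table 6 has no row between 3 and 6 months

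*Combined protocol and SAP*

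**What the plan says.** All of this is in section 7.1 of the combined protocol and SAP, except the scan schedule.

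- **Stopping rule (Futility Monitoring).** Enrolment stops "if there is less than 5% chance that the median PFS is more than that observed with historical therapy (6.8 months"). Looks are made at each accrual, with a minimum of 10 and a maximum of 30 patients from cohorts 1 and 2, at one patient per month.
- **Priors (Technical details).** PFS is exponential. The historical median has an "inverse gamma distribution with mean 6.8 months and standard deviation of 1 month". The experimental median has an inverse gamma prior with the same mean and a standard deviation of 10 months.
- **Purpose (Technical details).** "This rule was chosen to achieve a high early-stopping probability if the true median PFS is less than 6.8 months for the experimental treatment". The sentence goes on to claim a fairly low stopping probability above 6.8 months.
- **Table 6, "Operating characteristics of the futility monitoring rule".** The columns are scenario, true median, stopping probability, mean patients and duration. The relevant rows are "2 3 0.99 12.49 25.23", "3 6 0.23 26.46 38.92" and "4 7 0.11 28.19 40.55". No row lies between 3 and 6 months, and there is none at 6.8 (benchmark) or 10.5 (target).
- **Imaging (6.1.4.2).** "The first on-study imaging assessment should be performed at 6 weeks", then 12-weekly, or sooner on clinical grounds. At interim looks, section 7.1 censors event-free patients at their last visit assessed for progression.

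**The concern.** The sentence and the table disagree. A true median of 6 months is below 6.8, yet by Table 6 the trial runs to full enrolment in 1 − 0.23 = 77% of cases. Someone who relies on the sentence will think the rule protects patients across the whole range below the benchmark.

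The table does not let that reader find where protection ends. The stopping probability falls from 0.99 to 0.23 between two adjacent rows, and a median of 4 or 5 months is a case an ethics committee might well ask about.

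This matters because it is the only numerical stopping boundary in the plan. The early-termination criteria in section 5.8 are qualitative.

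**Working it through.** **1. Inputs (all from section 7.1).** Historical prior mean 6.8, SD 1. Experimental prior mean 6.8, SD 10. Cutoff 0.05. Looks at each accrual from 10 patients, maximum 30. One patient per month. Exponential PFS.

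**2. Prior parameters.** For an inverse gamma, shape a = (mean/SD)² + 2 and scale b = mean × (a − 1).
- Historical: a = 6.8² + 2 = 48.24; b = 6.8 × 47.24 = 321.2.
- Experimental: a = 0.68² + 2 = 2.462; b = 6.8 × 1.462 = 9.944.

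The central 95% ranges come out at 5.12–9.02 and 1.57–24.77 months, exactly as the SAP states.

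**3. The rule.** With d events and T patient-months of follow-up, the experimental median has posterior IG(2.462 + d, 9.944 + ln2 × T). The probability that it exceeds the historical median is an F distribution function with 2(2.462 + d) and 2 × 48.24 degrees of freedom, evaluated at [(9.944 + ln2 × T) × 48.24] / [(2.462 + d) × 321.2]. Setting this to 0.05 gives the boundary:

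| Events d | Stop if T is below (months) | Observed median at the boundary, ln2 × T/d |
|---|---|---|
| 10 | 52.8 | 3.66 |
| 20 | 124.3 | 4.31 |
| 24 | 153.6 | 4.44 |

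The estimated median must be well under 5 months before the rule stops, even late in the trial. A true median of 6 months will not often produce that.

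**4. Reproducing Table 6, then filling the gaps.** Simulation with exact event times, 8,000 trials per cell; ranges cover fixed and Poisson accrual.

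| True median | Table 6 | Simulated Pr(stop) | Simulated mean N |
|---|---|---|---|
| 3 | 0.99 | 0.99 | 12.3–12.6 |
| 4 | no row | 0.82–0.83 | 17.6–17.7 |
| 5 | no row | 0.48–0.49 | 23.0–23.2 |
| 6 | 0.23 | 0.23–0.24 | 26.5–26.6 |
| 6.8 | no row | 0.12–0.13 | 28.0–28.2 |
| 7 | 0.11 | 0.10 | 28.4 |
| 10.5 | no row | 0.01 | 29.8 |

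Table 6 rests on 1,000 simulations, so its standard error at 0.23 is √(0.23 × 0.77/1000) = 0.013. The agreement is within that. Separate runs gave 0.65 at 4.5 months, 0.35 at 5.5 and 0.47 at 5.

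**5. Sensitivity to the scan schedule.** Scans at weeks 6, 18, 30 and so on; progression dated at the detecting scan; event-free patients censored at the last scan; underlying (latent) median 6 months. The share of events found between scans, by death or symptom-led imaging, is not in the documents and is varied here.

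| Share found between scans | Pr(stop) |
|---|---|
| 0% | 0.06–0.07 |
| 25% | 0.10–0.11 |
| 50% | 0.16–0.18 |
| 75% | 0.23–0.25 |
| 100% | 0.31–0.32 |

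Two effects pull in opposite directions. Late detection removes events from each look and lowers stopping. Censoring at the last scan instead of the look date removes exposure and raises it: from 0.03 to 0.06 with no between-scan detection, and from about 0.24 to 0.31–0.32 with full detection.

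**The case against.** **The sentence is only a design aim, and the true figure is printed beside it.** Both are fair. Table 6 shows 0.23 at 6 months, so nothing is concealed at that value, and the sentence is borne out at 1 and 3 months. But it names 6.8 months as the dividing line, and the rule does not behave that way between roughly 4.5 and 6.8 months.

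**Rare stopping at 6 months may be acceptable.** This also stands. Section 4.3.3.1 puts the historical median at about 6 months, and the SAP's own historical prior runs from 5.12 to 9.02. The point concerns the description and does not show that the rule must be tightened. A 0.10 cutoff would raise stopping at 6 months to about 0.38–0.40, but would double it at 6.8, from 0.12 to 0.24. That is a trade-off for the trial team.

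**The rows at 6.8 and 10.5 are nearly bracketed already**, by 7 months (0.11) and by 10 and 11 months (0.01 each). True: the informative gap is 3 to 6 months. The other two cost nothing and are the design's own reference values.

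**A reader might infer that the 12-week scans make the rule weaker than Table 6 shows.** The documents do not support that as a general statement. It holds only if a modest share of events is found between scans. Deaths count as PFS events, section 6.1.4.2 allows earlier imaging, and section 6.1.4.5 calls for imaging of clinically unstable patients. At a 75–100% share, stopping is at or above 0.23. If the 6-month median is taken as scan-recorded PFS, stopping is 0.17 (none found between scans) to 0.24 (half), close to the table.

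**A reader might also infer that scan timing inflates the final test's false-positive rate.** That depends on how progression was timed in the historical data behind 6.8 months, which the documents do not say.

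**Conclusion.** The point holds as a mismatch between the SAP's description of its futility rule and the rule's operating characteristics. Table 6 is correct under its stated model; the sentence is not. The stopping probability is about 0.99 at 3 months and 0.82 at 4, but 0.47–0.49 at 5, 0.23 at 6 and 0.12 at 6.8. These figures rest on the SAP's own assumptions: exponential PFS, events seen when they occur, one accrual per month, and a look at each accrual from the tenth patient.

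The scan-schedule result is a sensitivity finding only. It gives 0.06 to 0.32 at a latent median of 6 months, on an assumed between-scan share and last-scan censoring. Its direction relative to Table 6 cannot be settled from the documents. At no point in that range is stopping at 6 months likely, so the conclusion about the sentence does not depend on it.

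**What to change.** 1. Reword the purpose sentence in section 7.1 (Technical details) to say that the rule stops with high probability only at true medians of about 4 months or less, and with probability about 0.23 at 6 months.
2. Add rows to Table 6 at 4, 5, 6.8 and 10.5 months.
3. As a sensitivity analysis, re-run Table 6 with scans at week 6 and then every 12 weeks, and with the SAP's last-visit censoring. Use a stated range of between-scan detection shares, and say whether the true median means underlying or scan-recorded PFS.

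The cutoff, the priors, the conjugate model and the sample size can stay as they are. The cost is one short simulation run and a wording change; the downside is that the stated protection reads as less favourable.

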5.0 METHODOLOGY

5.1 Study Population

5.1.1 Participant Inclusion Criteria

Participants are eligible to be included in the study only if all the following criteria apply:

1. Male/female participants who are at least 18 years of age on the day of signing informed consent with Pathologic findings supporting the clinical impression of anaplastic thyroid carcinoma will be enrolled in this study. Diagnosis may include consistent with or suggestive of terminology associated with: anaplastic thyroid carcinoma, undifferentiated carcinoma, squamous carcinoma; carcinoma with spindled, giant cell, or epithelial features; poorly differentiated carcinoma with pleomorphism, extensive necrosis with tumor cells present.
2. Stage IVB disease (no convincing evidence of metastatic disease outside of the neck) who have unresectable disease are eligible in groups 1 or 2. Previous excisional biopsy is permitted.
3. Stage IVB disease (no convincing evidence of metastatic disease outside of the neck) who have undergone complete resection of tumor (no convincing evidence of metastatic disease in the neck) are eligible in group 3
4. Patient must have completed external beam radiation with or without concomitant cytotoxic chemotherapy to participate in groups 1 and 2. Those who have completed these treatment after surgical resection of primary tumor may participate in group 3.
5. Patients may enroll only after completing radiation. Study drug may start from 2-6 weeks (+2 weeks) after radiation is completed and can only be started once radiation and chemotherapy-related toxicities are grade 2 or less (with the exception of

alopecia). If a subject is consented but AEs are not grade 2 or less by 8 weeks after RT is completed, that subject is not eligible and should not start pembrolizumab.

6. A female participant is eligible to participate if she is not pregnant (see Appendix 3), not breastfeeding, and at least one of the following conditions applies:
 - a. Not a woman of childbearing potential (WOCBP) as defined in Appendix 3
OR
 - b. A WOCBP who agrees to follow the contraceptive guidance in Appendix 3 during the treatment period and for at least 120 days after the last dose of study treatment.

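### The cohort 3 DFS clock starts at an undated disease-free status; if that date precedes the first pembrolizumab dose, DFS includes guaranteed event-free time

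*Combined protocol and SAP*

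**What the plan says.** The Analysis part of Section 7.1 defines three clocks in one paragraph.

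- PFS: "PFS will be calculated as the time from date of start of pembrolizumab to the earliest date of last clinic visit assessed for progression", progression or death.
- OS: "OS will be calculated as the time from date of start of pembrolizumab to the earliest date of death or last conduct".
- DFS: "DFS will be calculated as time from disease-free status to earliest date of last clinic visit assessed for disease", recurrence, metastasis or death.

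No section assigns a calendar date to disease-free status. Section 7.1 sends DFS through the same analysis as PFS (median with confidence interval, Kaplan-Meier, Cox regression) and mentions neither delayed entry nor a landmark. It also gives cohort 3 five subjects and a descriptive analysis. Section 3.2 lists median DFS in cohort 3 as an exploratory objective, while Section 7.1 groups DFS with the secondary objectives.

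The entry conditions are in Section 5.1.1. Criterion 3 says that stage IVB patients "who have undergone complete resection of tumor (no convincing evidence of metastatic disease in the neck) are eligible in group 3". Criterion 4 adds: "Those who have completed these treatment after surgical resection of primary tumor may participate in group 3". Criterion 5 states: "Patients may enroll only after completing radiation. Study drug may start from 2-6 weeks (+2 weeks) after radiation is completed". Sections 5.7 and 7.1 both replace patients who never receive pembrolizumab.

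**The concern.** A cohort 3 patient has to clear several hurdles in sequence before being counted: complete resection, completed radiation, continued freedom from disease at screening, and a first dose. A patient who recurs or dies before that dose is not in the DFS analysis. If the clock starts at an earlier hurdle, the time between it and first dose is event-free by construction for everyone analysed. Counting that time as DFS is immortal-time bias, and it acts in one direction only.

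Two things are at stake. The estimated median and landmark DFS rates would be too high by roughly the length of the pre-dose interval, and a constant shift given to every patient does not shrink with sample size. In addition, because the origin is not dated, the same five patients could yield materially different medians depending on a date chosen after the data are seen.

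**Working it through.** **The plan's own figures.** The documents state no figure for DFS. The one design calculation, for PFS in cohorts 1 and 2, reproduces:

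- Events = (z0.90 + z0.80)² / [ln(6.8/10.5)]² = 23.9, rounded up to 24.
- With 30 months of accrual, 12 months of follow-up and λ = ln2/10.5, P(event) = 1 − [exp(−12λ) − exp(−42λ)]/(30λ) = 0.803.
- N = 24/0.803 = 29.9, rounded up to 30. Power at 24 events is 80.1%.

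DFS does not enter this calculation, so the point below leaves it untouched.

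**Formula for the shift.** Let g be the time from the DFS origin to first dose, and T the disease-free time from first dose with median m. The time recorded under an earlier origin is g + T. Its median is m + g when g is constant. If g varies between patients, the median lies between m plus the smallest g and m plus the largest. With exponential T, the recorded 12-month rate is exp[−ln2·(12 − g)/m] instead of exp[−ln2·12/m]. Conversion: 1 week = 7/30.4375 = 0.23 months.

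**The gap g under each candidate origin**

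| Origin | Source of the interval | g (weeks) | g (months) |
|---|---|---|---|
| Screening scan | Section 6.1.4.1: at most 14 days before first dose | 0-2 | 0-0.46 |
| End of radiation | Section 5.1.1, criterion 5: 2-6 weeks plus a 2-week window | 2-8 | 0.46-1.84 |
| Resection | The 2-8 weeks above, plus an assumed 2-6 weeks from surgery to radiation and an assumed 3-7 weeks of radiation | 7-21 | 1.61-4.83 |

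Resection sums: 2 + 3 + 2 = 7 weeks and 6 + 7 + 8 = 21 weeks. The documents give neither assumed interval.

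The first row relies on Section 6.1.4.1. Footnote 1 of the Schedule of Activities words the same limit the opposite way (not less than 14 days). With the 28-day screening window, that reading would give 14-28 days, or 0.46-0.92 months (28/30.4375 = 0.92). The two passages need reconciling.

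**Illustration.** The documents give no expected DFS for cohort 3. Assume, purely as an example, m = 10.5 months from first dose:

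| Origin | Reported median (months) | Inflation | 12-month rate (45% from first dose) |
|---|---|---|---|
| Screening scan | 10.5-11.0 | 0-4% | 45-47% |
| End of radiation | 11.0-12.3 | 4-18% | 47-51% |
| Resection | 12.1-15.3 | 15-46% | 50-62% |

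A shorter true median makes the relative inflation larger. At an assumed 6.8 months it is 0-7%, 7-27% and 24-71% in the three cases.

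**After the change.** With the clock at first dose, or with patients joining the risk set only at first dose, the pre-dose contribution is zero and the shift disappears.

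**The case against.** The strongest reply is that the text does not say the clock starts at surgery. Disease-free status could be the status confirmed at screening. On the Section 6.1.4.1 timing the guaranteed time is then at most 14 days and may be nil. This stands, and it is why the size can only be given as a range.

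A reader might go further and infer that DFS is timed from resection and that every cohort 3 patient is therefore credited with several months. The documents do not support that as fact. Resection is a natural reading, but only one of three, and most of its interval comes from durations that the documents do not state. Nor should the shift be set against the 6.8-month median in Section 7.1. That is a historical PFS figure for unresected patients, and the plan compares nothing in cohort 3 with it.

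A second reply is that the objective in Section 3.2 concerns the whole sequence of surgery, radiation, chemotherapy and then pembrolizumab, so an origin before first dose may be intended. That is a legitimate estimand. It still needs delayed entry, because patients are observed only if they reach first dose, and Section 7.1 does not provide for it. Section 5.7 does require patients who are never dosed to be reported, but that does not return their events to the DFS estimate.

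A third reply is that nothing depends on the result: five patients, a descriptive summary, and no DFS hypothesis, comparator or stopping rule. This also stands and limits the importance of the point. Any median from five patients will be very imprecise. Cohort 3 is also a different population from cohorts 1 and 2, so its DFS would not be directly comparable with their PFS even on a common clock.

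**Conclusion.** The point holds in conditional form. Section 7.1 gives DFS an undated origin that differs from that of PFS and OS, and specifies no delayed entry. Any origin before first dose adds guaranteed event-free time for every cohort 3 patient and biases DFS upward. The size is about 0-0.5 months (screening scan, on the Section 6.1.4.1 timing), 0.5-1.8 months (end of radiation) or roughly 1.6-4.8 months (resection, with assumed surgery-to-radiation and radiation durations). The percentage figures rest further on assumed medians and, for the 12-month rates, on exponential DFS.

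This is a minor point. It concerns a five-patient descriptive cohort and has no bearing on the primary PFS analysis, its power or futility monitoring. It is more than a missing detail because on two of the three readings the rule as written gives an estimate that is too high.

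**What to change.** Change one sentence in Section 7.1: define DFS as time from the first pembrolizumab dose to the earliest of recurrence, metastasis or death, censored at the last disease assessment. If time from surgery or from the end of radiation is wanted, name that date and analyse with delayed entry (left truncation) at first dose. With five patients the early risk sets under delayed entry may be very small, so the first-dose definition is the more practical main analysis. In the same edit, reconcile the exploratory label for DFS in Section 3.2 with the secondary label in Section 7.1.

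The first-dose definition needs no new data, since PFS and OS already require that date. The delayed-entry option also needs the chosen earlier date recorded for each patient. The downside is that the reported DFS will be shorter.

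### The evaluable set requires a follow-up scan and is not reconciled with the primary analysis set, so treated patients who die unscanned can be left out of PFS

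*Combined protocol and SAP*

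**What the plan says.** Section 7.1 describes the analysis population in three places.

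- Evaluable Analysis Set: "Our evaluable patient population will be subjects who start pembrolizumab and have one follow up imaging visit to assess for disease progression". The replacement rule follows: "Subjects who do not start pembrolizumab will be replaced". Section 5.7 likewise limits replacement to people who never received a dose.
- Analysis: "Cohorts 1 and 2 will consist of our primary analysis set". This sentence has no scan condition.
- Power Calculation: "with 30 evaluable patients we would have 80.0% power using 1-sided 10% alpha for a one-sample log rank test".

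On timing, Section 6.1.4.2 says: "The first on-study imaging assessment should be performed at 6 weeks", counted from the first dose, with a window of 7 days either way. On the endpoint, the primary objective in Section 3.1 counts death as a PFS event from the start of pembrolizumab, and the Analysis text in Section 7.1 includes the date of death. (The one-line definition under Power Calculation leaves death out.) The comparator is a fixed figure: "Based on historical data, the median PFS for unresected patients is 6.8 months". OS is to be analysed in the same way as PFS.

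**The concern.** Membership of the evaluable set is decided after time zero, by getting as far as a scan. A participant who starts pembrolizumab and dies before any imaging has failed on the primary endpoint but does not meet the definition. Nothing in the plan counts that death as an event or brings the participant back.

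The exclusion depends on the outcome, and its effect runs one way: removing early deaths can only lengthen the apparent PFS. Section 4.3.3 itself notes that events in this cancer come quickly. The trial has one arm, so no control group is subject to the same exclusion. If OS is analysed in the same set, early deaths would also leave an endpoint that needs no scan.

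Because the plan contains both a scan-conditioned set and an unconditioned one, the choice between them could also be made after the data are known.

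**Working it through.** **Inputs.** From Section 7.1: null median 6.8 months, target 10.5 months, exponential PFS, 30 patients at one per month, 12 months of further follow-up, one-sided alpha 10%, 24 events. From Section 6.1.4.2: first scan at 42 days, which is 42/30.44 = 1.38 months. Assumed, because the documents do not give it: q, the share of PFS events before week 6 in patients who are never imaged.

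**1. The plan's own figures.** Hazard ratio = 6.8/10.5 = 0.648.
- Events = (1.2816 + 0.8416)² / (ln 0.648)² = 23.9, rounded up to 24.
- Power at 24 events = Φ(√24 × 0.4345 − 1.2816) = 80.1%.
- Expected events at a median of 10.5, with uniform accrual over 30 months plus 12 months of follow-up, = 24.1.

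The stated 80.0% and 24 events are reproduced.

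**2. Events before the first scan is due.** P = 1 − 2^(−1.38/median).
- Median 6.8: 13.1%, or 3.9 of 30.
- Median 10.5: 8.7%, or 2.6 of 30.

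These are all PFS events, not only deaths.

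**3. Median in the retained patients.** Removing a share q of those events leaves survival S(t)/(1 − qP) after week 6. Setting this to one half gives:

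retained median = 6.8 − 6.8 × ln(1 − qP)/ln 2

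**4. Type I error.** Trials were simulated under the null with the statistic (E − O)/√E, where O is observed events and E is events expected at a median of 6.8, and a critical value of 1.2816.

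| q (assumed) | Mean patients lost of 30 | Retained median (months) | Type I error |
|---|---|---|---|
| 0 | 0 | 6.80 | about 8.5% |
| 10% | 0.4 | 6.93 | about 9.5% |
| 25% | 1.0 | 7.13 | about 11% |
| 50% | 2.0 | 7.47 | about 15% |
| 100% (upper bound) | 3.9 | 8.18 | about 24% |

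With nothing removed, the test runs slightly below its nominal 10%, so the first row is the right reference.

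**5. The quantity the Analysis text reports.** That text gives a posterior probability that the median exceeds 6.8 months. Using the plan's prior for the experimental median and a true median of 6.8, its typical value rises from 0.43 (q = 0) to 0.50 (25%), 0.57 (50%) and 0.70 (100%).

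**6. Shortfall against 30 evaluable.** At a true median of 10.5, q of 25% and 50% loses 0.7 and 1.3 patients, and expected events fall from 24.1 to 23.4 and 22.8. At 100% they fall to 21.5.

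**The case against.** **The plan may already intend all treated patients.** The primary-set sentence has no scan condition, the Technical details compute PFS for each patient, and no sentence says outright that PFS or OS is estimated in the evaluable set. This stands in part. A reader might infer that exclusion is settled, but the documents support only an unreconciled conflict. The link to the evaluable set comes from the power statement and from its being the only set defined by patient-level criteria. The plan never says that all treated patients are analysed.

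**Patients who decline are mostly kept.** A reader might infer that anyone who deteriorates before week 6 is lost. The documents do not support that. Section 6.1.4.5 calls for imaging of clinically unstable participants, Section 6.1.4 counts unscheduled images, and Section 6.1.4.3 expects a scan at discontinuation. Progression first seen on the week-6 scan also stays in. The loss is mainly unscanned early deaths.

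**The largest figures are not expected values.** A type I error of 24% and a median of 8.2 months require every event before week 6 to go unimaged, contrary to those same imaging rules. Entry at ECOG 0 to 1, with baseline imaging within 14 days before the first dose, also argues for a low q. At 10% the error is still under the nominal level.

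**The test is named only in the power statement.** The Analysis text plans a median with a 95% interval and a posterior probability, without a success threshold. That is correct, so the type I figures describe the design test; step 5 shows the same direction for the planned summary.

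**The benchmark may carry the same selection.** If the historical series also required a scan, the bias in the comparison would be smaller. The documents do not say.

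**Conclusion.** The concern holds as a conflict in the plan that permits outcome-dependent exclusion. If the evaluable set is used for PFS, the direction is certain: leaving out unscanned early deaths favours the drug. The size is not known. For assumed q of 10 to 50%, the retained median under the null rises by 0.1 to 0.7 months, and type I error goes from about 8.5% to between 9.5% and 15%; 8.2 months and 24% are bounds. These figures rest on the plan's exponential model, a first scan at exactly 42 days, and a 6.8-month benchmark that was not itself conditioned on a scan.

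The shortfall in evaluable patients is real but small, about one patient at q of 25 to 50%. A reader might infer a serious loss of power, and the calculation does not support that. Because the deletion favours the drug, the rejection rate at a true median of 10.5 goes up, from about 80% to 84% and 86% at those shares.

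**What to change.** In Section 7.1:

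- Define the primary PFS and OS set as all cohort 1 and 2 participants who receive at least one dose of pembrolizumab, and reconcile the three statements about populations accordingly.
- Count death before the first scan as a PFS event on the date of death.
- For PFS, censor at day 1 those alive with no post-baseline assessment, and report how many there are. Such a participant adds no PFS information, so the number needs to be visible.
- Follow OS to death or last contact, whether or not imaging was done.
- State power for 30 treated patients. About 80% and 24 events are unchanged, and the replacement rule then matches the sample size.
- Keep the scan-based evaluable set only as a labelled sensitivity analysis.

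The cost is SAP wording, with no added patients or procedures. The PFS estimate may come out slightly less favourable.
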